with intentional sharing of the peer mentor's experiences to offer new ideas and validate shared struggles. The ILSM conversation guides were developed collaboratively with the 4 peer mentor interventionists and study co-investigators. A fidelity measure of adherence to the ILSM format was developed and used to rate sessions via audio-recordings (Other Attachment IIC). The measure, based on the Yale Adherence and Competence Scale(62), uses a 4-point scale to rate the skill (1 representing "very poor" to 4 representing "skilled") and extensiveness (1 representing "not discussed" to 4 representing "a lot of discussion" [e.g., >15 minutes]) with which ILSM conversations are delivered. A rating of 2 or greater on both skill and extensiveness was considered adequate fidelity to the intervention. Fidelity to general communication and peer support skills (e.g., validation, sharing, avoidance of medical advice) were also rated on the 1 to 4 point "skill" scale with a score of 3 or greater indicating fidelity to the intervention. Two research assistants were trained on use of the fidelity measure until inter-rater agreement was >80%. Among 20 sessions rated using the measure, 85% demonstrated adequate fidelity to the ILSM model and 72.5% of general skills were performed with adequate fidelity. These ratings clearly demonstrate peer mentors were able to incorporate PREVAIL content into their contacts with participants.

Outcomes and safety. Comparisons of outcomes between the intervention and enhanced usual care control groups were not conducted because any finding would be an unreliable estimate of the true effect given the small sample size.(11) The R34 randomized control group allowed pilot testing of all necessary protocols in preparation for this R01 study. Across the entire sample, 24% of participants reported any post-enrollment suicide attempt at 3 months according to the Columbia Suicide Severity Rating Scale.(63) Suicidal ideation according to the Beck Scale for Suicidal Ideation improved from 23.3 (SD 7.6) at baseline to 6.6 (SD 7.7) at 3 months.(64) Despite limited power, improvements on belongingness measures of loneliness and perceived rejection, but not emotional support, were statistically significant at 3 months.(65) There was also statistically significant improvement on a measure of hopelessness, but not hope, at 3 months.(66, 67) These findings demonstrate feasibility of measuring the primary outcomes and potential mediators in a larger trial.

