Peer mentors will be provided study cell phones to contact participants. These cell phones will be password encrypted, and will be stored in a combination lockbox when not in use. Peer mentors may use these cell phones to text participants in order to schedule meetings if they are unable to reach them by phone call. Peer mentors will keep

these study cell phones turned off outside of business hours when they are not meeting with a participant, and will maintain an outgoing voicemail greeting that provides the National Suicide Prevention Lifeline phone number.

Peer mentors may email participants for the purpose of scheduling mentorship sessions. Peers will use email for scheduling only if the participant has no working phone available where they can be reached. All email communications from peer mentors will be sent from Level 2 email accounts.

SELECTION AND ENROLLMENT OF PARTICIPANTS

Inclusion Criteria

The goal of the study inclusion and exclusion criteria is to identify a broadly representative sample of inpatient psychiatric patients at high risk for suicide based on a suicide attempt or suicidal ideation prior to admission. Including only those with a suicide attempt would limit the generalizability of the intervention. Recruitment from inpatient units facilitates the initial in-person peer support contact in a safe setting and ensures some intervention has taken place prior to when patients are at maximal risk immediately following discharge. (77)

Patients will be eligible for the study if they: 1) are age 18 years or older, 2) are currently admitted to an inpatient psychiatric unit and have medical record documentation of suicidal ideation or suicide attempt at the time of admission, 3) have a Beck Suicide Scale score of 5 or higher for the 1-week period prior to admission, 4) are fluent in English, and 5) are able to be reached reliably by telephone. The age and language criteria are necessary because peer mentors will be English-speaking adults.

Exclusion Criteria

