Based on estimates from the participating sites and pilot study results, we anticipate 480 (60% of 800) patients will be admitted to UM per year with medical record documentation of suicidal ideation or a suicide attempt. We anticipate that the number of patients admitted to Henry Ford Macomb and Wyandotte with medical record documentation of suicidal ideation or a suicide attempt will be similar to that seen at the previous Henry Ford Kingswood site (n=720 per year, or 60% of 1200). Of these, we estimate 60% will not meet eligibility criteria and 22% will refuse, such that 216 could be recruited per year. Enrollment of 490 participants during 3 years of recruitment is therefore feasible. The PI of the study ([name]) will oversee recruitment via weekly calls with HF site PI ([name]) and coordinators from both institutions. Informed consent will be obtained from all participants (see Protection of Human Subjects). Baseline measures (see D2j) will be completed at the time of enrollment, prior to study arm assignment.

Telephonic Screening and Recruitment During COVID-19 Pandemic

Due to health concerns and limitations imposed on in-person research activities during the COVID-19 pandemic, screening and recruitment of subjects will take place telephonically during this time. Potentially eligible patients will be identified via chart review, and approved for recruitment by their attending provider as usual. Research staff will obtain eligible and approved patient(s)' on-unit cell phone number from inpatient unit staff and call the patient(s) to pitch the study using an oral script. Interested patients will receive a study packet from unit staff that includes (1) Consent to be Screened, (2) Consent to be a Part of a Research Study, (3) a printed copy of study measures, (4) printed copies of peer mentor bios, and (5) a study timeline handout that includes study team contact information. Patients will not have access to smart phones, tablets, or private computers on the inpatient units; therefore, all enrollment activities must take place over the phone, and a waiver of documentation of informed consent must be utilized for these enrollments. Subjects will keep the paper copies of consent forms for their records.

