The primary outcome is to determine the effectiveness of the PREVAIL peer mentorship intervention for reducing suicide attempts and suicidal ideation among recently hospitalized adult psychiatric patients at high risk for suicide. In a two-site, randomized controlled trial (N=490), participants in the 3-month peer mentorship intervention arm will be less likely to report a suicide attempt on the Columbia Suicide Severity Rating Scale (CSSR-S) and will report less severe suicidal ideation on the Beck Scale for Suicidal Ideation (BSI) over the 6 months following enrollment compared to those in an enhanced usual care control condition.

1. Suicide attempts (measured by the Columbia Suicide Severity Rating Scale) [Time Frame: 6-months]
Any suicide attempt as measured according to an electronic self-report version of the Columbia Suicide Severity Rating Scale (CSSR-S). The definition of suicide attempt for the primary outcome will consist of any actual suicide attempt, aborted suicide attempt, or interrupted suicide attempt according to the CSSR-S.
2. Change in suicidal ideation (measured by the Beck Suicide Scale (BSS)) [Time Frame: Baseline, 6-months]
Patient's current suicidal ideation as measured by the Beck Suicide Scale (BSS). The BSS is a self-report 19-item scale preceded by five screening items. The BSS and its screening items assess thoughts, plans and intent to commit suicide. All 24 items are rated on a three-point scale (0 to 2). Total scores could range from 0 to 48 (if the screening items are included). No specific cut-off scores exist to classify severity. Increasing scores reflect greater suicide risk.

Secondary Outcomes

1. Medically serious suicide attempts (measured by the medical record) [Time Frame: 6-months]
Any suicide attempt as notated in the patients electronic medical record. The definition of suicide attempt for the primary outcome will consist of any actual suicide attempt, aborted suicide attempt, or interrupted suicide attempt.

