Based on our pilot study findings and those of other randomized controlled trials of psychosocial interventions that included suicide attempts as a primary outcome (91, 92, 109), we powered the study with the assumption that frequency of suicide attempts at 6 months will be 22% in the intervention arm vs. 36% in the control arm. We will enroll 490 patients in total, and assuming a 25% dropout rate, 368 (184 per group) will provide primary outcome data. The proposed sample size is expected to provide 84% power to detect the desired difference between the two groups based on a two-sided 0.05 level test. The estimate of effect is based on an assumption that the effect of PREVAIL will be similar to that reported in a trial of cognitive behavioral therapy for suicide among suicide attempters (N=120) where the re-attempt rate at 6 months was 25% among intervention recipients vs. 40% for controls. (91) Although there is no prior literature comparing the effects of peer support to psychotherapy on suicide-specific outcomes, two meta-analyses have concluded the effects of peer support on depression are similar to psychotherapy. (49, 51) Our estimate of effect is conservatively less than that found for brief psychodynamic interpersonal therapy, where in one trial (N=119) the self-harm rate at 6 months was 9% in the intervention arm compared to 28% for controls. (92) For the primary outcome of suicidal ideation according to the Beck Scale for Suicidal Ideation at 6 months and measures of hope and belongingness at 3 months (Aim 2), our sample of 368 will provide 90% power to detect a standardized effect size (Cohen's d) of .34. For the mediator analysis, the proposed sample size is expected to provide 80% power to detect a significant mediator assuming that the intervention explains about 2% of the variance of the mediator (corresponding to "small" effect based on Cohen's criteria), and about 7% of the variance of suicide ideation is explained by the mediator adjusting for the intervention effect, or vice versa based on joint significance testing for the mediation effect. (110)

Data Analysis

Baseline Analyses

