We will examine the randomization process to determine if there were any between-group differences at baseline, particularly in variables that are thought to be potentially associated with suicide attempts or ideation. T-tests or chi-square analyses, as appropriate, will be used to test for differences in the following baseline variables between study groups: age, severity of suicidal ideation prior to admission, burdensomeness, hope/hopelessness, and measures of belongingness. When there are significant differences in the distribution of these variables, they will be included as covariates in multivariable analyses. Balance is expected for sex and recent suicide attempt due to randomization by minimization.

Data Verification/Univariate Analyses: We will examine the distribution of all study variables for extreme values, missing data, variances, possible coding errors, skewness and whether or how to categorize skewed data. We will describe means (SD) for the continuous measures and frequencies of dichotomous outcomes by study group for each assessment time for the entire sample and for each of the study sites, separately.

Primary Outcome

Primary analyses will determine the effectiveness of PREVAIL in decreasing the risk of any suicide attempt and in decreasing suicidal ideation at 6 months post-randomization. Primary analytic cohort will be "intent to treat", such that all randomized participants will be included according to their original study arm assignment, regardless of whether they subsequently drop out of participation in the intervention. Secondary analyses will be conducted using a "per protocol" cohort where only participants who complete 6 or more peer encounters will be compared to those assigned to the EUC arm. We will evaluate predictors of compliance by defining 6 or more peer encounters as compliance and will also obtain complier average difference (a.k.a. complier average causal effect) assuming a balanced proportion of compliance between arms. The estimates of the three analytic cohorts (intent to treat, per protocol and compliance average difference) will provide more robust understanding of the effect of PREVAIL. (106)

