Bivariate/Multivariate Analyses: To test for intervention effects at 6 months on the primary outcomes, a logistic regression model will be used for the dichotomous outcome of suicide attempt (as assessed by CSSR-S) and a multiple regression model will be used for suicidal ideation (as assessed by BSI). Each model will include the study arm as the primary predictor and will also include study site, gender, and prior suicide attempt, which were the balancing variables used in randomization. We will also adjust for additional covariates that show imbalances in baseline analyses. Outcomes at 6

[figure not shown]
months post-randomization will be our primary analysis in order to assess whether the intervention has lasting effects, but we will also assess immediate effects at 3 months using similar analytic approaches.

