Approach to Missing Data

Our initial analyses will only use observed data. When data are missing for items within scales, we will use recommended imputation procedures rather than excluding participants from the analyses. For missing follow-up assessments, we will check if missingness is associated with any baseline variables including sites, and will include any such baseline variables in the models evaluating the intervention effect described above. In addition, as described under Effect Over time, the mixed-effects model is expected to provide an unbiased estimate of the intervention effect if missingness is at random. As a secondary analysis, we will also conduct an analysis that imputes missing data. We will likely have some missing baseline values in addition to missing follow-up assessments. Thus we will conduct multiple imputations based on chained equations (sequential regression multivariate imputation) to impute both baseline and follow-up data and will summarize the data using appropriate combination rules. (107, 108)

REGULATORY, ETHICAL AND STUDY OVERSIGHT CONSIDERATIONS

Informed Consent Process

Patients who appear to meet study inclusion and exclusion criteria based on review of medical records and consultation with the attending psychiatrist will be approached by the research assistant (RA) to describe the study, provide information about the randomization and 3 and 6-month assessments, as well as the risks, benefits, and limitations to confidentiality. Patients who state they are interested will be asked to complete a brief cognitive screener to assess whether they are substantially cognitively impaired and therefore unable to give informed consent. Patients who are not substantially cognitively impaired will complete a pre-screening consent form allowing study staff to administer the Beck Suicide Scale and items 4 and 5 of the Columbia Suicide Scale. Patients who have a score >5 on the Beck Suicide Scale will be eligible to participate and obtain informed consent. During the informed consent process, the study will be described and patients will have ample and repeated opportunities to ask questions.

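### Baseline suicidal ideation should be a fixed covariate in the primary 6-month ideation regression; the plan admits it only through two data-driven rules

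*Combined protocol and SAP*

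**What the plan says.** Under Bivariate/Multivariate Analyses, the SAP tests the 6-month primary outcomes with a logistic model for attempts and a multiple regression for ideation: "Each model will include the study arm as the primary predictor and will also include study site, gender, and prior suicide attempt". Baseline ideation is not a fixed term, but two rules can bring it in.

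- **Imbalance.** Baseline Analyses tests a list of variables that includes ideation severity before admission: "When there are significant differences in the distribution of these variables, they will be included as covariates in multivariable analyses". Bivariate/Multivariate Analyses repeats the rule.
- **Missingness.** Approach to Missing Data checks which baseline variables are associated with missing follow-up and "will include any such baseline variables in the models evaluating the intervention effect described above".

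The response is labelled in two ways. Primary Outcomes, item 2, reads "Change in suicidal ideation (measured by the Beck Suicide Scale (BSS)) [Time Frame: Baseline, 6-months"; Sample Size reads "For the primary outcome of suicidal ideation according to the Beck Scale for Suicidal Ideation at 6 months", and the model text also refers to 6 months.

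The baseline score can be read in two ways as well. Patients must "have a Beck Suicide Scale score of 5 or higher for the 1-week period prior to admission" (Inclusion Criteria), and Baseline Analyses uses the same pre-admission period, whereas Primary Outcomes describes current ideation.

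Secondary Outcomes applies a similar regression to hope and belongingness. Effects over time adds a mixed model that uses baseline ideation, as an additional analysis.

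**The concern.** Baseline score is usually a natural covariate for a later score on the same scale. In a linear model it removes outcome variance whether or not the arms happen to differ at baseline and whether or not it predicts dropout. Under randomization, a 5% imbalance test admits it in about one trial in twenty, whatever its prognostic value. The plan can therefore leave out a covariate that it has already paid to collect, and part of a primary model is settled after data are seen. Score or change, and pre-admission or current baseline, are also left for the analyst to resolve. At stake are some precision on a primary outcome and a clean specification of its model.

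**Working it through.** **Inputs from the documents.** Sample Size gives 490 enrolled, 25% dropout, 184 per arm analysed, and 90% power at d = 0.34 for ideation. The two-sided 0.05 level is stated there for attempts and is taken to apply to ideation too.

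**Assumed, because the documents do not give them.** r is the correlation of baseline with 6-month BSS, given site, gender and prior attempt; the range is 0.2 to 0.5. The odds ratio (OR) for missing follow-up per SD of baseline BSS ranges from 1.0 to 1.5.

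**1. The plan's own figure.** Noncentrality = d × √(n/2) = 0.34 × √92 = 3.261 on 366 degrees of freedom, which gives 90.2%. The stated 90% reproduces as an unadjusted comparison of 6-month scores.

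**2. Baseline BSS always included.** The residual SD shrinks by √(1 − r²), so the standardized effect becomes 0.34/√(1 − r²).

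| r | Effect | Power |
|---|---|---|
| 0.2 | 0.347 | 91.3% |
| 0.3 | 0.356 | 92.6% |
| 0.4 | 0.371 | 94.4% |
| 0.5 | 0.393 | 96.4% |

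If site, gender and prior attempt explain 5% of the 6-month variance, power is 91.6% without baseline and 92.6, 93.8, 95.4 and 97.1% with it.

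**3. Comparison with the plan's rules.** The simulation randomized 490 and lost 25% to follow-up, with dropout depending on baseline BSS only. Baseline BSS was added if its arm test or its missing-versus-observed test had p < 0.05 (the SAP states no threshold for the second). There were 20,000 trials per cell. Entries are power in %, plan / always included.

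| Dropout OR per SD | BSS enters | r = 0.2 | r = 0.3 | r = 0.4 | r = 0.5 |
|---|---|---|---|---|---|
| 1.0 | 10% | 89.9 / 90.7 | 90.3 / 92.3 | 90.8 / 94.3 | 91.2 / 96.4 |
| 1.2 | 44% | 90.4 / 91.0 | 91.4 / 92.6 | 92.5 / 94.4 | 93.3 / 96.4 |
| 1.3 | 71% | 90.9 / 91.2 | 91.7 / 92.3 | 93.4 / 94.3 | 94.7 / 96.2 |
| 1.5 | 97% | 91.3 / 91.4 | 92.6 / 92.7 | 94.0 / 94.1 | 96.0 / 96.2 |

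The 10% entry rate at OR 1.0 is what two independent 5% tests give: 1 − 0.95² = 9.75%. The Monte Carlo standard error of a difference is about 0.2 points or less. Type I error under the plan was 4.5 to 5.1% in all 16 null cells.

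**4. Score or change.** Let Y be the 6-month score and X the baseline score. If Y = a + b·arm + c·X + e, then Y − X = a + b·arm + (c − 1)·X + e. The arm coefficient b and the residuals are the same, so the label stops mattering once X is in the model. This requires the covariate and the score subtracted to be the same BSS.

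**5. Missing baseline values.** Approach to Missing Data expects some. If complete-case fitting cut the sample to 176 per arm (8/184 = 4.3% lost), power at r = 0.2 would be 90.1%, and the gain would be gone.

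**6. The missingness rule.** A null simulation added a second baseline variable, correlated 0.3 with BSS, with dropout OR 2.0 per SD in the control arm and 1.0 in the intervention arm. BSS was always included. Type I error without the second variable was 6.9%, against 5.4% under the plan's rules, when that variable's correlation with the outcome was 0.3; at 0.5 it was 10.6% against 5.7%. A separate run gave 6.5 to 10.9% against about 5%. With OR 1.5 against 1.0 the difference was negligible (5.7% against 5.6%).

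**The case against.** The strongest reply is that nothing is broken. The stated power reproduces, type I error holds, and the gain rests on two quantities that the documents do not supply. Low r is plausible: entry truncates the scale from below, and in the pilot BSS "improved from 23.3 (SD 7.6) at baseline to 6.6 (SD 7.7) at 3 months". At r = 0.2 to 0.3 the gain is 2 points or less in every cell, and at OR 1.5 it is within simulation error. The simulated comparator also carried BSS alone. The real rules could admit correlated variables such as hopelessness and recover some precision, so the gains are approximate and may be too high. All of this stands. It limits the size of the point, but it does not make imbalance or dropout the right entry criterion.

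That the mixed model already uses baseline ideation is true but does not answer the point, because the SAP makes the 6-month regression primary. Nor are the hope and belongingness models an arbitrary extension: Sample Size gives them the same N, d and power, so steps 1 and 2 carry over, with r unknown for each measure.

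A reader might infer three stronger things that the documents do not support:

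- **That the data-driven rules inflate type I error.** The simulations show no inflation.
- **That the primary analysis is an unadjusted change score and so falls short of 90% power.** Only the outcome label says change. The SAP's primary model and power statement concern 6 months, and the between-arm difference in decrease from baseline is tested only under Effects over time, as an additional analysis.
- **That covariates added for missingness should also leave the primary model.** Step 6 shows that this can cost validity when dropout differs strongly between arms.

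**Conclusion.** The point holds as a specification and efficiency improvement. The primary ideation model omits a pre-randomization covariate that is already collected: "Baseline measures (see D2j) will be completed at the time of enrollment, prior to study arm assignment", and a BSS is needed for entry. Always including it raises power from 90.2% to between 91.3 and 96.4% for r from 0.2 to 0.5. Against the plan's rules the gain is about 1 to 5 points with no link between ideation and dropout, and close to zero with a strong link. Always including it was never worse in the cells computed. These figures assume the stated d and N, linear effects, no loss of patients through missing baseline values, and values of r and the dropout OR that cannot be checked from the documents. The unclear response label and baseline period remain at any r. The attempt model was not computed, and nothing is claimed about it.

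**What to change.** 1. In Bivariate/Multivariate Analyses, list baseline BSS as a fixed covariate in the ideation model beside site, gender and prior attempt, whatever the imbalance or missingness checks show.
2. State which pre-randomization BSS it is (the week before admission, or current at enrollment). Say how a missing value is handled, so that no patient with a 6-month outcome is dropped.
3. Name the 6-month BSS as the response and align Primary Outcomes, item 2. Note that, with the same baseline score in the model, the arm estimate is identical for score and change.
4. For this model, replace covariate selection by baseline significance tests with the pre-specified covariate.
5. In Secondary Outcomes, include the baseline value of each hope and belongingness measure in its own model.

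Keep the inclusion of baseline variables associated with missing follow-up. The covariate set will then still depend partly on observed dropout, which is an acceptable price for protection against differential loss.

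The cost is SAP wording only; no new data or patients are needed.
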